8.2.2. Other Secondary Efficacy Analyses

This section describes the planned analyses for the secondary efficacy outcome measures. Analyses of mortality will be described in Section 9.4 and analyses of markers of inflammation and coagulation will be described in Section 9.7.

Analyses of the other secondary outcome measures will be performed by treatment only and repeated for specified subgroups described in Table 6. As with the analyses described in Section 8.2.1, tabular summaries will mimic the structure of the main tabular summaries planned for each outcome with the modification that stratified estimates will be provided in separate rows. Forest plots will display confidence intervals of outcomes/estimates across subgroups, where applicable.

Ordinal Scale Outcomes

Analyses will evaluate the time to improvement of at least one point on the clinical status 8-point ordinal scale. The time to 1 point improvement (at least 1 point drop from baseline) will be defined as the elapsed time (in days) from Study Day 1 to the day prior to the earliest recorded day at which a subject reaches at least a 1-point improvement up to and including Study Day 60. Any subjects whose last assessment in the study is prior to an observed improvement will be censored at the day of their last observed Clinical Status score. Subjects who complete follow-up but do not experience improvement will be censored at the day of their Study Day 60. All deaths that occur on or before Study Day 60 (and prior to any observed improvement) will be considered censored at Day 60.

Refer to Table 6 for a list of covariates and subgroup analyses for this endpoint. Refer to Table 7 for imputation methods to be applied to this endpoint.

An alternative definition of improvement will also be used where improvement will be defined as a decrease of at least two points on the 8-point scale compared to the baseline value (e.g., from 5 to 3; from 5 to 2). The timing and censoring definitions will follow a strategy similar to the above one-point improvement.

The Cox proportional hazards model will be performed to test whether the survival curves differ between treatments (with respect to improvement endpoints). The median time to event and CI in each treatment group will be summarized along with the treatment hazard ratio estimate and p-value (Table 32). Differences in time-to-event endpoints by treatment will also be summarized with Kaplan-Meier curves (Figure 9). Number at risk, hazard ratio and log rank test p-values will be presented on the figures.

The analyses (and tabular and graphical summaries) will be repeated using the outcome of time to improvement in two categories of the ordinal scale (Table 33, Figure 10).

The number and proportion of subjects in each ordinal score by baseline ordinal score will be presented by treatment at Baseline and Study Visit (not necessarily actual) Study Days 3, 5, 8, 11, 15, 22, 29, 60 (Table 35). Additionally, the change from baseline in ordinal scale (e.g., proportion who have a 1-, 2-, 3-, or 4-point improvement or 1-, 2-, 3-, or 4-point worsening), or no change, will be presented at all post-dose Study Visit Days (Table 34). Figures by study day visits will present grouped bar charts by point changes with side-by-side bars for each treatment (Figure 18).

The mean change from baseline at Study Days 3, 5, 8, 11, 15, 22, 29, and 60 will be summarized by treatment (Table 35).

The main analysis of the primary endpoint will be repeated using the ordinal score on Study Days 15 and 29 instead of Day 8 using complete data, adjusting for baseline severity and steroid use. The analysis will be repeated for baseline severity of disease, baseline steroid use, baseline use of emerging COVID-19 treatments, and duration of symptoms subgroups. Each subgroup will be considered separately, and the estimated treatment odds ratio from the proportional odds model with corresponding 95% and 80% confidence intervals and the p-value will be presented for each subgroup. A forest plot will be generated to display the overall treatment odds ratio and CI from each of the within-stratum analyses. Results for Day 15 will be presented in Table 17, Figure 4, and Figure 5 while results for Day 29 will be presented in Table 18, Figure 6, and Figure 7. These analyses will be repeated for the ITT population and results will be presented in Table 20 and Table 21. Odds ratios between the binary progression strata from the proportional odds model are reported in Table 24, Table 25, Table 26, Table 27 for mITT population and ITT population for Study Days 15 and 29.

Oxygenation

Oxygen days will be defined as the number of days where the ordinal score > 4 up to and including Study Day 29. The total number of days will be the sum of all reported days, regardless of whether the days occur consecutively or in disjoint intervals. For planned gaps between study days, the day of the qualifying Study Day and the days to the next planned Study Day will be included in the total number of days. The Post-Discharge Supplemental Oxygen CRF questions regarding days of oxygenation (including ECMO, invasive ventilation, non-invasive ventilation, high-flow oxygen devices, and all other oxygen delivery devices) will be used for any time period the subject is not hospitalized at the study hospital. See Section 6.5 for the plan for handling subjects who do not have data through Study Day 29 or die prior to Study Day 29.

Duration of oxygenation days will be summarized in a table using medians and quartiles by treatment (Table 36). Bee swarm plots of oxygen days by treatment will be generated (Figure 19).

Refer to Table 6 for a list of covariates and subgroup analyses for this endpoint. Refer to Table 7 for imputation methods to be applied to this endpoint.

Non-Invasive Ventilation/High-Flow Oxygen

Non-invasive ventilation/high flow-oxygen days or worse will be defined as the number of days where the ordinal score is > 5 up to and including Study Day 29. The total number of days will be the sum of all reported days, regardless of whether the days occur consecutively or in disjoint intervals. For planned gaps between study days, the day of the qualifying Study Day and the days to the next planned Study Day will be included in the total number of days. The Post-Discharge Supplemental Oxygen CRF questions regarding days of non-invasive ventilation or high-flow oxygen will be used for any time period the subject is not hospitalized at the study hospital. See Section 6.5 for the plan for handling subjects who do not have data through Study Day 29 or die prior to Study Day 29.

Duration of non-invasive ventilation/high flow oxygen days or worse will be summarized in a table using medians and quartiles by treatment (Table 37). Bee swarm plots of non-invasive ventilation/high flow oxygen days by treatment will be generated (Figure 20).

The incidence and duration of new Non-Invasive Ventilation/High-Flow Oxygen use or worse will be analyzed by treatment (Table 40). The numerator will include only subjects in category 5 or below at enrollment who change to a category 6, 7, or 8. The denominator will only include subjects with an actual baseline ordinal score of 5 or below at enrollment. The number of subjects reporting new use of Non-Invasive Ventilation/High-Flow Oxygen and the incidence rate along with 95% and 80% CIs estimated using the Blaker method will be reported.

Refer to Table 6 for a list of covariates and subgroup analyses for this endpoint. Refer to Table 7 for imputation methods to be applied to this endpoint.

Invasive Mechanical Ventilation/ECMO

Ventilator / ECMO days will be defined as the number of days where the ordinal score > 6 up to and including Study Day 29. The total number of days will be the sum of all reported days, regardless of whether the days occur consecutively or in disjoint intervals. For planned gaps between study days, the day of the qualifying Study Day and the days to the next planned Study Day will be included in the total number of days. The Post-Discharge Supplemental Oxygen CRF questions regarding days of ECMO or invasive ventilation will be used for any time period the subject is not hospitalized at the study hospital. See Section 6.5 for the plan for handling subjects who do not have data through Study Day 29 or die prior to Study Day 29.

Duration of Invasive Mechanical Ventilation/ECMO days will be summarized in a table using medians and quartiles by treatment (Table 38). Bee swarm plots of Invasive Mechanical Ventilation/ECMO days, and days hospitalized by treatment will be generated (Figure 21).

The incidence of new Invasive Mechanical Ventilation/ECMO use will be analyzed by treatment (Table 41). The numerator will only include subjects in category 6 or below at enrollment who change to a category 7 or 8. The denominator will include subjects with a baseline ordinal score of 6 or below. The number of subjects reporting new use of Invasive Mechanical Ventilation/ECMO and the incidence rate along with 95% and 80% CIs estimated using the Blaker method will be reported.

Refer to Table 6 for a list of covariates and subgroup analyses for this endpoint. Refer to Table 7 for imputation methods to be applied to this endpoint.

Proportion of Subjects Alive and Without Respiratory Failure at Study Day 29

The proportion of subjects alive and without respiratory failure at Study Day 29 will be defined as the proportion of subjects with an ordinal score < 7 at any time between Day 26 through Day 32 (Visit window for Study Day 29 Visit). The proportion of subjects with respiratory Failure or death at Day 29 will also be provided. These proportions will be presented by treatment along with 95% and 80% Blaker CIs. Treatment differences will be evaluated using a logistic regression and the p-value will be presented (Table 31).

Refer to Table 6 for a list of covariates and subgroup analyses for this endpoint. Refer to Table 7 for imputation methods to be applied to this endpoint.

Time to Mechanical Ventilation or Death up to and Including Day 29

The time to mechanical ventilation or death up to and including Day 29 will be defined as the elapsed time (in days) from Study Day 1 to date of mechanical ventilation or death. Any subjects whose last assessment is prior to obtaining the event and prior to Day 26 (beginning of Day 29 window) will be censored at the date of their last observed assessment. For the sensitivity analysis of this endpoint, subjects whose last assessment is

prior to obtaining the event and who were discharged to a location other than LTAC, hospice care, or other hospital will be considered recovered and censored at Day 29. For both primary and sensitivity analysis of this endpoint, subjects who complete follow-up will be censored Day 29. Events that occur after Day 29 will be censored at Day 29. A table will present median time to event along with corresponding 95% and 80% confidence intervals for each treatment along with the hazard ratio estimate and score test p-value from a Cox-proportional hazard model (Table 42). The Cox model will include as covariates baseline ordinal score, baseline CRP value, continuous age, and baseline dexamethasone use. Differences in time-to-event endpoints by treatment will be summarized with Kaplan-Meier curves (Figure 11). Analyses will be performed on the mITT population for those subjects who at baseline have an ordinal score of 5 or 6, CRP<150 mg/L, and age<85 years and results will be reported in Table 42. This analysis will be repeated for all subjects in the mITT population and results will be reported in Table 43.

Refer to Table 6 for a list of covariates and subgroup analyses for this endpoint. Refer to Table 7 for imputation methods to be applied to this endpoint.

Hospitalization

Duration (in days) of hospitalization will be defined as the number of days subject is hospitalized for COVID-19-related reasons starting from the date of randomization. It will be calculated as the total number of days hospitalized, including readmissions for COVID-19-related reasons. It will also be calculated as the total number of days hospitalized, including any readmissions regardless of cause. See Section 6.5 for the plan for handling subjects who do not have data through Day 29 or die prior to Day 29.

Duration of hospitalization days will be summarized in a table using medians and quartiles by treatment (Table 39). Bee swarm plots of days hospitalized by treatment will be generated, where subjects whose days are imputed due to death are grouped separately from subjects who do not die (Figure 22).

Refer to Table 6 for a list of covariates and subgroup analyses for this endpoint. Refer to Table 7 for imputation methods to be applied to this endpoint.

Individual listing of all primary and secondary endpoints is provided in Listing 14.

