OBJECTIVES	ENDPOINTS (OUTCOME MEASURES)			
29.				
 Non-invasive ventilation/high-flow oxygen: Non-invasive ventilation/high-flow oxygen use up to Day 29. Incidence and duration of new non-invasive ventilation or high-flow oxygen use through Day 29. 	• Days of non-invasive ventilation/high- flow oxygen (if applicable) up to Day 29.			
 Invasive Mechanical Ventilation/ ECMO: Ventilator/ECMO use up to Day 29. Incidence and duration of new mechanical ventilation or ECMO use through Day 29. 	 Days of invasive mechanical ventilation/ECMO (if applicable) up to Day 29. 			
 Proportion of subjects alive and without respiratory failure at Day 29. 	 Proportion of subjects who did not meet either of the following two categories on Day 29: 7. Hospitalized, on invasive mechanical ventilation or ECMO; 8. Death. 			
 Hospitalization: Duration of hospitalization (days). 	• Days of hospitalization up to Day 29.			
 Mortality: 14-day mortality. 29-day mortality. Time to death up to Day 29. 60-day mortality. 	• Date and cause of death (if applicable).			
• Markers of inflammation and coagulation.	 C-reactive protein (CRP), ferritin, D- dimer, and fibrinogen on Day 1; Days 3, 5, 8, and 11 (while hospitalized); and Days 15 and 29 (if attends in-person visit or still hospitalized). 			
 2. To evaluate the safety of risankizumab as compared to the control arm as assessed by: Cumulative incidence of SAEs through Day 60. Cumulative incidence of Grade 3 and 4 clinical and/or laboratory AEs through Day 60. 	SAEs.Grade 3 and 4 AEs.			

OBJECTIVES	ENDPOINTS (OUTCOME MEASURES)		
 Discontinuation or temporary suspension of study product administration (for any reason). Changes in white blood cell (WBC) count with differential, hemoglobin, platelets, creatinine, total bilirubin, alanine aminotransferase (ALT), aspartate aminotransferase (AST), and international normalized ratio (INR) over time (analysis of lab values in addition to AEs noted above). 	 Episodes of early discontinuation or interruption of study product administration. WBC with differential, hemoglobin, platelets, creatinine, total bilirubin, ALT, AST, and INR on Day 1; Days 3, 5, 8, and 11 (while hospitalized); and Days 15 and 29 (if attends in-person visit or still hospitalized). 		
Exploratory			

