3.1.2.2. Other Secondary Objectives

1. To evaluate the clinical efficacy of different investigational therapeutics as compared to the control arm as assessed by:
 - Clinical severity
 - 8-Point Clinical Status Ordinal scale:
 - Time to an improvement of 1 category and 2 categories from Study Day 1 (baseline) up to and including Study Day 60 using clinical status,
 - Clinical status using 8-point ordinal scale at Study Days 1, 3, 5, 8, 11, 15, 22, and 29,
 - Mean change in the ordinal score from Study Day 1 to Study Days 3, 5, 8, 11, 15, 22, and 29
 - Oxygenation:
 - Supplemental oxygen use up to and including Study Day 29.
 - Non-invasive ventilation/high-flow oxygen:
 - Non-invasive ventilation/high-flow oxygen use up to and including Study Day 29,
 - Incidence and duration of new non-invasive ventilation or high-flow oxygen use up to and including Study Day 29 (i.e., a subject with a baseline ordinal score of 5 who worsens to an ordinal score of 6, 7, or 8).

-
- Invasive Mechanical Ventilation/ extracorporeal membrane oxygenation (ECMO):
 - Ventilator/ECMO use up to and including Study Day 29,
 - Incidence and duration of new mechanical ventilation or ECMO use up to and including Study Day 29 (i.e., a subject with a baseline ordinal score of 5 or 6 who worsens to an ordinal score of 7).
 - Proportion of subjects alive and without respiratory failure at Day 29
 - Hospitalization:
 - Duration of hospitalization (days) up to and including Study Day 29.
 - Mortality:
 - 14-day mortality (up to and including Day 15),
 - 28-day mortality (up to and including Day 29),
 - 59-day mortality (up to and including Day 60),
 - Time to death up to and including Day 29.
 - Markers of inflammation and coagulation.
2. To evaluate the safety of different investigational therapeutics as compared to the control arm as assessed by:
- Cumulative incidence of serious adverse events (SAEs) up to and including Study Day 60,
 - Cumulative incidence of Grade 3 and 4 clinical and/or laboratory adverse events (AEs) up to and including Study Day 60,
 - Discontinuation or temporary suspension of study product administration (for any reason),
 - Changes in white blood cell (WBC) count with differentials, hemoglobin, platelets, creatinine, total bilirubin, alanine aminotransferase (ALT), aspartate aminotransferase (AST), estimated glomerular filtration rate (eGFR) and international normalized ratio (INR) over time.

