3.2. Endpoints

Primary Endpoint

The default primary endpoint is clinical status (8-point ordinal scale) on Study Day 8:

1. Not hospitalized, no new or increased limitations on activities;
2. Not hospitalized, but new or increased limitation on activities and/or requiring new or increased home oxygen, CPAP, or BiPAP;
3. Hospitalized, not requiring new or increased supplemental oxygen - no longer requires ongoing medical care;
4. Hospitalized, not requiring new or increased supplemental oxygen - requiring ongoing medical care (COVID-19 related or otherwise);
5. Hospitalized, requiring new or increased supplemental oxygen;
6. Hospitalized, requiring new or increased non-invasive ventilation or high-flow oxygen devices;
7. Hospitalized, on invasive mechanical ventilation or extracorporeal membrane oxygenation (ECMO);
8. Death.

Key Secondary Endpoints

One of the key secondary endpoints is time to sustained recovery (up to and including Study Day 60) and is defined as the first day on which the subject satisfies 1 of the following 3 categories from the clinical status ordinal scale (and does not return to a score of ≥ 4 up to and including Study Day 60):

1. Not hospitalized, no new or increased limitations on activities;
2. Not hospitalized, but new or increased limitation on activities and/or requiring new or increased home oxygen, CPAP, or BiPAP;
3. Hospitalized, not requiring new or increased supplemental oxygen - no longer requires ongoing medical care.

The other key secondary endpoint is whether the subject did not satisfy one of the following two categories from the ordinal scale up to and including Study Day 29. This analysis will only be completed for those subjects with baseline ordinal score of 5 or 6:

7. Hospitalized, on invasive mechanical ventilation or ECMO;
8. Death.

If the key secondary endpoints are different than what is covered in this master SAP, it will be highlighted for each individual investigational intervention in the corresponding stage-specific appendix.

Other Secondary Endpoints

The other secondary endpoints are:

Efficacy

- Time (days) from Study Day 1 to the first day for which a subject is assessed to be at least 1 category lower (improvement) than the subject's baseline ordinal score up to and including Study Day 60;
- Time (days) from Study Day 1 to the first day for which a subject is assessed to be at least 2 categories lower (improvement) than the subject's baseline ordinal score up to and including Study Day 60;

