- Clinical status assessed using ordinal scale on Study Days 1, 3, 5, 8, 11, 15, 22, and 29;
- Change in clinical status using change in ordinal scale from Study Day 1 to Study Days 3, 5, 8, 11, 15, 22, and 29;
- Days of supplemental oxygen or worse (i.e., ordinal score of 5, 6, 7, 8) up to and including Study Day 29;
- Days of non-invasive ventilation/high-flow oxygen or worse (i.e., ordinal score of 6, 7, 8) up to and including Study Day 29;
- Whether a subject who has a baseline ordinal score of 5 requires new non-invasive oxygen use or worse (i.e., ordinal score of 6, 7, 8) during the study up to and including Study Day 29 (incidence);
- Days a subject who has a baseline ordinal score of 5 has an ordinal score of 6 or greater up to and including Study Day 29;
- Days of invasive mechanical ventilation/ECMO or worse (i.e., an ordinal score of 7 or 8) up to and including Study Day 29;
- Whether subject who has a baseline ordinal score of 5 or 6 requires new invasive ECMO use or worse (i.e., ordinal score of 7 or 8) during study up to and including Study Day 29 (incidence);
- Days a subject who has a baseline ordinal score of 5 or 6 has an ordinal score > 6 up to and including Study Day 29;
- Whether a subject is alive and without respiratory failure (ordinal score < 7) at Study Day 29;
- Time (days) to ventilation or death from Study Day 1 up to and including first 29 days of being on study.
- Days of hospitalization from date of admission up to and including Study Day 29.
- Values of C-reactive protein (CRP), ferritin, D-dimer, lactate dehydrogenase (LDH), and fibrinogen on Study Days 1, 3, 5, 8, and 11 (while hospitalized); and Study Days 15 and 29 (if attends in-person visit or still hospitalized).

Safety

- Whether a subject died from Day 1 up to and including Study Day 15.
- Whether a subject died from Day 1 up to and including Study Day 29.
- Whether a subject died from Day 1 up to and including Study Day 60.
- Time (days) to death from Study Day 1 up to and including Study Day 29.

- Whether a subject experienced at least one SAE up to and including Study Day 60.
- Whether a subject experienced at least one Grade 3 or Grade 4 AE up to and including Study Day 60.
- Episodes of early discontinuation or interruption of study product administration.

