6.5. Missing Data

6.5.1. General Guidelines Regarding Handling of Missing Data

All attempts will be made to collect all data per the protocol. Efforts to minimize loss-to-follow-up will be considerable. Chart review will be performed for lost-to-follow-up subjects to obtain data related to the subjects' clinical status, oxygen use, or death status after discharge. However, small amounts of missing data may occur. In order to conduct mITT and ITT analyses for primary and secondary outcomes, missing data will be imputed in the manners described below in [Table 7](#). Prior to applying the imputation rules described in [Table 7](#), an endpoint review committee (ERC) may meet to adjudicate the primary endpoint and the key secondary endpoints for each study stage, such as Day 8 ordinal scores for subjects discharged to hospice, another hospital, or long-term care facilities. Any ERC reviews will be performed prior to database lock and all committee members will be blinded to treatment assignments. If an ERC is used, an ERC charter will be prepared prior to any reviews.

For the primary analysis of ordinal score at Day 8, the following imputations will be performed prior to multiple imputation:

- If a subject is discharged from the hospital to another location other than LTAC, hospice care or other hospital, has intermittent missing ordinal score and reported an ordinal score of 1 or 2 after the missing score then:
 - The intermittent missing ordinal score is imputed as 1 if the scores reported before and after the missing value are both 1 and no change in oxygen use or hospitalization status after discharge to a location other than hospice, long term acute care or other hospital.
 - The intermittent missing ordinal score is imputed as 2 after discharge to a location other than hospice, long term acute care or other hospital if the subject doesn't fall into the category above and subject is not hospitalized at the time point.
- LOCF will be used for remaining intermittent missingness of ordinal scores for the next planned assessment.
- All missing scores after death will be assigned an ordinal score of 8.
- Subjects that terminated from the study with known discharge to a location other than hospice, LTAC or other hospital at their last assessment will be assigned a score of 2 for all timepoints after last assessment.

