Table 40: Incidence of Secondary Outcomes – Non-Invasive Ventilation/High Flow Oxygen Free Days or Worse through Day 29 — mITT Population

Outcomes	Treatment	Population at Risk ^a		New Cases ^b		Incidence Rate		
		n	%	n	%	Estimate ^c	95% CI ^d	80% CI ^d
Primary Analysis	Treatment A (N=X)	x	x.x	x	x.x	x.xxx	x.xxx, x.xxx	x.xxx, x.xxx
	Treatment B (N=X)	x	x.x	x	x.x	x.xxx	x.xxx, x.xxx	x.xxx, x.xxx
Subgroup Analysis								
Repeat for each sensitivity and subgroup category as detailed in Table 6 and Table 7.								
N=Number of subjects in modified intent-to-treat (mITT) population. n= Number of unique subjects that satisfies the row criteria. ^a Population at risk is defined as all subjects with a baseline ordinal score of 5 or below. ^b New cases are defined as subjects with a baseline ordinal score of 5 or below that progress to an ordinal score of 6, 7, or 8. ^c The incidence rate is the proportion of the population at risk that have new cases. ^d Confidence intervals for the incidence rate estimated using Blaker method.								

Table 41: Incidence of Secondary Outcomes – Ventilator/ECMO Days or Worse through Day 29 — mITT Population

Outcomes	Treatment	Population at Risk ^a		New Cases ^b		Incidence Rate		
		n	%	n	%	Estimate ^c	95% CI ^d	80% CI ^d
Primary Analysis	Treatment A (N=X)	x	x.x	x	x.x	x.xxx	x.xxx, x.xxx	x.xxx, x.xxx
	Treatment B (N=X)	x	x.x	x	x.x	x.xxx	x.xxx, x.xxx	x.xxx, x.xxx
Subgroup Analysis								
Repeat for each sensitivity and subgroup category as detailed in Table 6 and Table 7.								
N=Number of subjects in modified intent-to-treat (mITT) population. n= Number of unique subjects that satisfies the row criteria. ^a Population at risk is defined as all subjects with a baseline ordinal score of 6 or below. ^b New cases are defined as subjects with a baseline ordinal score of 6 or below that progress to an ordinal score of 7 or 8. ^c The incidence rate is the proportion of the population at risk that have new cases. ^d Confidence intervals for the incidence rate estimated using Blaker method.								

Table 42: Time to Mechanical Ventilation or Death through Day 29 — mITT Population with Baseline Ordinal Score of 5 or 6, CRP<150 mg/L, and age<85 years

Analysis/Subgroup	Treatment	Number of Subjects to Mechanical Ventilation or Death ^d		Median Time Until Event			Hazard Ratio			P-value ^e
		n	%	Estimate	80% CI	95% CI	Estimate	80% CI	95% CI	

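### Table 41 counts deaths without ventilation as new ventilator/ECMO use, and no planned table gives the incidence of new ventilation itself

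*SAP*

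**What the plan says.** Protocol Section 3 (Table 3) lists as a secondary objective "Incidence and duration of new mechanical ventilation or ECMO use through Day 29". It attaches no ordinal score to this item. On the protocol's scale, invasive ventilation/ECMO is category 7 and death is category 8.

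The SAP gives more than one definition:

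- Section 3.1.2.2 (objectives) explains the event as "a subject with a baseline ordinal score of 5 or 6 who worsens to an ordinal score of 7".
- Section 3.2 (endpoints) records, for subjects with baseline 5 or 6, whether each one "requires new invasive ECMO use or worse (i.e., ordinal score of 7 or 8) during study up to and including Study Day 29".
- Section 8.2.2 (analysis) states "The numerator will only include subjects in category 6 or below at enrollment who change to a category 7 or 8" and "The denominator will include subjects with a baseline ordinal score of 6 or below". It introduces the analysis as the incidence of new ventilation/ECMO use and labels the count the same way, without mentioning death.
- Table 7, row 9 (missing data) treats a subject whose last observed score is 7 or above as being on invasive ventilation/ECMO through Day 29.
- Table 41, footnote b, defines new cases as "subjects with a baseline ordinal score of 6 or below that progress to an ordinal score of 7 or 8".

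Section 6.5.1 adds "All missing scores after death will be assigned an ordinal score of 8". Nothing makes score 8 conditional on earlier ventilation.

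**The concern.** The objective and the analysis name different events. Under Section 3.1.2.2, a subject on low-flow oxygen who dies without ever being intubated has not had the event. Under Sections 3.2 and 8.2.2 and Table 41, that subject has, and the text reports the case as new ventilator/ECMO use.

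Two things are at stake. The rate labelled as new ventilation would be too high by the proportion of at-risk subjects who die unventilated. And the quantity the protocol asks for would not appear in the report. SAP Section 4.1 says this proof-of-concept trial should inform the sample size and endpoint selection of a larger trial. A ventilation rate that includes unventilated deaths is a poor input for that purpose.

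**Working it through.** The documents state no figure for this endpoint, so there is nothing to reproduce. The check is a comparison of definitions, followed by illustrative arithmetic.

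**1. Is Table 41's event the complement of the key secondary endpoint?** Section 3.2 defines that endpoint, for baseline 5 or 6, as "whether the subject did not satisfy one of the following two categories from the ordinal scale up to and including Study Day 29", the two categories being 7 and 8. Table 30's n is therefore the subjects never at 7 or 8 by Day 29, and Table 41's new cases are those ever at 7 or 8 by Day 29. Eligible baseline scores are 5, 6 or 7 (Protocol Section 5.1), so 6 or below equals 5 or 6, except for the few baseline-4 subjects that the table shells allow for. With complete follow-up and no such subjects, the two counts sum to N.

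Toy arm (assumed): 80 at risk, 15 ventilated, 11 deaths, 5 of them never ventilated.

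- Table 41: 15 + 5 = 20, or 20/80 = 25.0%.
- Table 30: 80 − 20 = 60, or 75.0%.
- New ventilation itself: 15/80 = 18.8%.
- Adding 2 to 5 event-free baseline-4 subjects gives 20/82 = 24.4% to 20/85 = 23.5% in Table 41.

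**2. Does another planned table give the incidence of score 7?**

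| Output | Content |
|---|---|
| Tables 22–27 | Splits of the score at Days 8, 15 and 29 only |
| Table 35 | Score distribution on set days |
| Tables 30, 31, 42, 43 | Ventilation-or-death composites |
| Table 38 | Days with score above 6, death included |
| Table 54 | Deaths, not split by prior ventilation |
| Listings 13, 14 | Subject-level data, no summary |

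None does. Subtracting deaths from Table 41 does not recover it: in the toy arm 20 − 11 = 9, not 15, because the 6 subjects who were ventilated and then died are in both counts.

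**3. Size of the overstatement (assumed rates).** Reported rate = ventilated + unventilated deaths.

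- 15% + 3% = 18%; 3/15 = 20% too high.
- 15% + 8% = 23%; 8/15 = 53% too high.

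**4. Effect on the comparison (assumed rates).** Let new ventilation be 20% on control and 10% on active (risk ratio 0.50), with unventilated death d equal in both arms. Reported ratio = (10 + d)/(20 + d).

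| d | Reported risk ratio | Never ventilated among new use, control | Same, active |
|---|---|---|---|
| 0% | 0.50 | 0% | 0% |
| 3% | 13/23 = 0.57 | 3/23 = 13% | 3/13 = 23% |
| 5% | 15/25 = 0.60 | 5/25 = 20% | 5/15 = 33% |
| 10% | 20/30 = 0.67 | 10/30 = 33% | 10/20 = 50% |

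A count of score 7 alone gives 0.50 in every row.

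**5. Days.** Table 38 works the same way. An unventilated death on Day 3 contributes 29 − 3 + 1 = 27 days of score above 6.

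**The case against.** The strongest reply is that Section 3.1.2.2 is the outlier. Its parallel item for non-invasive ventilation includes death (scores 6, 7 or 8), and every later statement of the invasive endpoint uses 7 or 8, so the objective may simply have lost its final words. The composite is also disclosed: Section 3.2 and the titles of Tables 38 and 41 say or worse, and footnote b spells it out. Counting death as the worst state stops early death from looking favourable. All of this stands as a defence of having a composite. It does not reconcile the objective with the analysis, justify Section 8.2.2's label, or supply the incidence of new ventilation.

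Some stronger inferences are not supported:

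- *The protocol defines the event as score 7.* It gives no score; only SAP Section 3.1.2.2 does.
- *Table 41 merely repeats Table 30.* The event and horizon are the same, but Table 41 gives crude proportions with 80% and 95% Blaker intervals, its own missing-data rule and a denominator of 6 or below. Table 30 gives Kaplan-Meier percentages and adjusted logistic regression for baseline 5 or 6.
- *Opposite movements in ventilation and death cannot be seen.* Some can. If intubation falls and total deaths do not change, Table 41 can fall while Table 54 stays flat; if a shift adds deaths, Table 54 rises. Tables 22–27 and 35 also separate 7 from 8 on fixed days. What escapes both Tables 41 and 54 is a shift among subjects who would have died anyway. For example, ventilation of 20% versus 14% with unventilated death of 3% versus 9% gives 23% in both arms of Table 41, and total deaths are equal if the 6 points are subjects who would otherwise have died ventilated.
- *The days total in Table 38 is an error.* Section 3.2 defines it openly as score 7 or 8.

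**Conclusion.** The plan is wrong as written on this endpoint. The SAP's objective and its analysis define new ventilation/ECMO differently, the analysis text labels a ventilation-or-death count as new use, and no planned table reports the incidence of new ventilation. The deaths affected are those by Day 29, without ventilation, among subjects with baseline score 6 or below; subjects with baseline 7 are outside Table 41.

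The direction is certain, since including unventilated deaths can only raise the reported rate. The size is not known. The 18% to 23% against 15%, and the risk ratios of 0.57 to 0.67 against 0.50, rest on assumed rates and show the mechanism only. The documents do not support a claim that the trial's reported rate will be materially wrong. The endpoint is secondary and descriptive, with no planned test. The primary analysis, key secondary analyses and sample size are unaffected.

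**What to change.** 1. Reconcile SAP Sections 3.1.2.2, 3.2 and 8.2.2, Table 7 row 9 and Table 41 footnote b on one definition of new ventilation/ECMO.
2. In Table 41, report per arm the subjects with baseline 6 or below whose first score of 7 occurs by Day 29. Give death without prior ventilation its own row, because it is a competing event and should be neither merged with ventilation nor treated as censoring.
3. Keep the 7-or-8 row only if it is relabelled as new ventilation/ECMO or death, and change the wording in Section 8.2.2 to match.
4. Leave the ventilation-or-death composites in Tables 30, 31, 42 and 43 as they are.
5. Optionally, show days at score 7 beside the existing total in Table 38.

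The cost is SAP wording and two rows per arm. The ordinal scores and death dates needed are already collected.
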